- s. When the Vital Status is determined, the subject should be asked if they have undergone a heart and/or liver transplant or implantation of cardiac mechanical assist device. If a subject indicates that they have had a transplant and they are still enrolled in the study, they should be removed from the study.
- In the event of early study discontinuation, the site staff will follow-up on the subject's vital status/transplant status 60 months after randomization/assignment date.
- u. Only countries listed in Appendix 5 may screen/enroll subjects in Cohort B. Upon availability of Day -30 disease confirmation results, subjects in Cohort B may return to the study site for Day 0 visit procedures.
- v. Cohort A: On Day 0, subjects in Cohort A will be blindly assigned to tafamidis meglumine 20 mg or 80 mg.
 Cohort B: On Day 0, subjects in Cohort B will be assigned to open label tafamidis 61 mg (or tafamidis meglumine 80 mg if unavailable).
- w. Cohort B only: Collect a genomic banked biospecimen. If missed, collect at the next available time point when biospecimens are being collected in conjunction with a subject visit.
- x. Cardiac biomarkers NT-proBNP and Troponin I sample collection effective after Protocol Amendment 4. Study subjects enrolled prior to Protocol Amendment 4 are required to sign an updated informed consent prior to providing blood sample for cardiac biomarker assessment.
- y. See Appendix 7 for Additional sample and banked biospecimen collection for newly enrolling subjects in specific countries. These samples will be used to support identification and characterization of serum, plasma, or urinary biomarkers of transthyretin amyloidosis. This collection introduced in Protocol Amendment 5 is relevant only to subjects participating in countries listed in Appendix 6.

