5.5.1. Dose-reduction

A one-time dose reduction to 20 mg tafamidis meglumine will be permitted for subjects after switching to 61 mg tafamidis.

Cohort A blinded dose reduction

In the event that subjects experience adverse events that may be associated with the tolerability of treatment with tafamidis that may impact dosing adherence, they should return to the clinic with their medication. If the investigator assesses that the tolerability issue is persistent and anticipated to impact dosing adherence and that the subject's safety is not compromised by continuing treatment, then the subject may request blinded treatment re-assignment to a lower dose. Only subjects assigned to 80 mg tafamidis in B3461045 after 30 months of placebo in Study B3461028 will be permitted one blinded dose-reduction to 20 mg.

The site personnel will enter the subject's study-specific identification (SSID) number into the IRT system and request blinded dose-reduction. The IRT system will provide a new container number for blinded treatment re-assignment for this subject.

If the subject was receiving the 80 mg dose in Study B3461045 after 30 months of placebo in Study B3461028, then the re-assignment will be to 20 mg. All other subjects will be maintained on the previously assigned dose but will still receive a new container number in order to maintain the blind.

If tolerability issues continue after the blinded re-assignment, the investigator has the option to discontinue dosing for this subject and to terminate study participation. In the event of early study discontinuation, the site staff will follow-up on the subject's vital status/transplant status 60 months after randomization into B3461045.

Cohort A & B open label dose reduction

In the event that subjects experience adverse events that may be associated with the tolerability of treatment with tafamidis that may impact dosing adherence, they should return to the clinic with their medication. If the investigator assesses that the tolerability issue is persistent and anticipated to impact dosing adherence and that the subject's safety is not

compromised by continuing treatment, then the subject may request treatment re-assignment to a lower dose. All subjects will be permitted one open label dose-reduction to 20 mg.

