If a subject does not return for a scheduled visit, every effort should be made to contact the subject. The site should make a minimum of 3 documented phone calls followed by a registered letter inquiring about the reason for lack of return for the scheduled appointment. In any circumstance, every effort should be made to document subject outcome, if possible, including the subject's vital status/transplant/cardiac mechanical assist device status through 60 months following the Screening visit. The investigator should inquire about the reason for withdrawal, request that the subject return for a final study visit (if applicable) and to return all unused investigational product(s), and follow-up with the subject regarding any unresolved adverse events (AEs).

If the subject withdraws from the study, and also withdraws consent for disclosure of future information, no further evaluations should be performed, and no additional data should be collected, except for ascertaining vital status/transplant/cardiac mechanical assist device status at 60 months after Screening. The sponsor may retain and continue to use any data collected before such withdrawal of consent. Subjects requesting withdrawal should be informed that withdrawal of consent for follow-up will jeopardize the public health value of the study. At the time of withdrawal, subjects will be asked about the contribution of possible adverse events to their decision to withdraw consent and any adverse event information elicited will be documented. Preferably the subject should withdraw consent in writing and, if the subject or the subject's representative refuses or is physically unavailable, the site should document and sign the reason for the subject's failure to withdraw consent in writing.

6.4.1. Subject Withdrawal for Heart or Liver Transplantation or Implantation of Cardiac Mechanical Assist Device

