Subjects may be on a transplant list at the time of randomization/enrollment in the study. However, if a subject chooses to accept a donor organ transplant during the study or undergoes implantation of a cardiac mechanical assist device, they will stop taking blinded study medication and be discontinued from study participation prior to the transplant operation. Vital status/transplant status for the subject will be established through 60 months following the Screening visit. Subjects who discontinue from the study due to transplantation or implantation of a cardiac mechanical assist device will be handled in the statistical analysis as described in Section 9.2.1.

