# 4.4. Other Analysis Sets

The "Combined Mortality Analysis Set" will include all subjects in the ITT-Analysis Set from B3461028. Mortality analyses in study B3461045 for Cohort A subjects will combine data from subjects in study B3461028, including subjects who died, discontinued in B3461028, or didn't enroll into B3461045 (ie, ITT Analysis Set from B3461028) with mortality data through participation in the B3461045 study. This analysis set will be referred to as "Combined Mortality Analysis Set".

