# 5.3. Methods to Manage Missing Data

Other than standard approaches for missing dates for adverse events, no data imputation will be performed in the study. Missing data from Cohort A subjects who ended participation in B3461045 study without achieving the completion criteria of sustainable access to tafamidis by prescription, and allowed to return to the study and continue participation until they reach protocol defined study completion will not be imputed. Adverse events reported in the CRF that occurred between the time a subject ended the participation and subsequently returned will be evaluated for treatment-emergence in the same manner as adverse events that occurred during the study participation.

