# 6. ANALYSES AND SUMMARIES

# 6.1. Primary Endpoint(s)

#### 6.1.1. All-cause Mortality

For Cohort A subjects, time to all-cause mortality will be calculated from Day 1 of the Study B3461028 based on the "Combined Mortality Analysis Set" as defined in Section 4.4. All-cause mortality will be analyzed using SAS Proc Lifetest; p-values will be from the log-rank test. Kaplan-Meier survival curves for each treatment group along with median survival times (if applicable) will be presented comparing tafamidis/tafamidis group with placebo/tafamidis group.

All-cause mortality will also be analyzed using Cox proportional hazards model with treatment, NYHA baseline classification, and TTR genotype (variant and wild-type) as factors. Subjects who discontinue for transplantation (ie, heart transplantation and combined heart and liver transplantation) or for implantation of a cardiac mechanical assist device, will be handled in the same manner as death. Data from subjects who drop out for a liver-only transplantation will be handled in the same manner as the data from all other censored subjects.

To examine the potential effect of including heart transplantation or cardiac mechanical assist device as "deaths" in the all-cause mortality analysis, a sensitivity analysis will be performed treating all transplantation or cardiac mechanical assist device in the same manner as any other censored observation.

For Cohort B, since subjects in this Cohort will all be administered the same dose, only overall descriptive statistics will be provided. Kaplan-Meier survival curve along with median survival time (if applicable) will be presented.

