# 6.2.1. Cardiovascular-related Mortality

For both Cohort A and B, cardiovascular-related mortality will be analyzed separately similar to all-cause mortality detailed in Section 6.1.1. Cardiovascular relatedness will be based on an evaluation and clinical judgment of the MedDRA preferred terms.

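### SAP 6.1.1 gives no censoring date for Cohort A all-cause mortality, and on the usual reading of SAP 4.4 deaths after early exit go uncounted although the protocol seeks early leavers' vital status

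*SAP*

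**What the plan says.** **Endpoint and test.** SAP 3.1 lists all-cause mortality as a primary endpoint. SAP 5.1 tests it for Cohort A, two-sided at 0.05. SAP 6.1.1 starts the clock on Day 1 of B3461028 and specifies the log-rank test and a Cox model. Heart transplant and cardiac device implantation count as death. Liver-only transplant data "will be handled in the same manner as the data from all other censored subjects", but no date is given at which a subject is censored. SAP 5.3 adds none. The sample code in SAP Appendix 2 has only a duration and a status flag.

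**Extent of the data.** SAP 4.4 takes the whole parent ITT set, including subjects who discontinued there or never entered the extension, and combines it "with mortality data through participation in the B3461045 study". Cardiovascular mortality inherits the rule: "cardiovascular-related mortality will be analyzed separately similar to all-cause mortality detailed in Section 6.1.1" (SAP 6.2.1).

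**Vital status of early leavers.** The Schedule of Activities footnotes ask sites for "vital status/transplant status 60 months after randomization/assignment date". Protocol 5.5.1 asks for "vital status/transplant status 60 months after randomization into B3461045", under both blinded and open-label dose reduction. Protocol 6.4 keeps this check even after consent to further disclosure is withdrawn: no more data, "except for ascertaining vital status/transplant/cardiac mechanical assist device status at 60 months after Screening". Protocol 6.4 also provides for a medical-release form and registry searches. The SAP does not mention these data.

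**The concern.** A time-to-event endpoint needs a start, an event and a censoring date. Here the third is missing for a tested primary endpoint, and the nearest substitute appears to stop at exit from the study. Two consequences follow.

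- Two analysts could build different duration variables from the same SAP. One could censor at the last visit, another at the last date known alive. Subjects who left Cohort A and later returned (SAP 5.3) are a further case with no stated rule.
- If deaths after exit are dropped, the Kaplan-Meier curves rest on the assumption that leavers have the same prognosis as stayers. Exits for persistent tolerability problems (Protocol 5.5.1) or inability to keep to the visit schedule (Protocol 6.4) make a worse prognosis plausible, though the documents do not show it. Survival would then be overstated, while the data to check this are ones the protocol already asks sites to obtain.

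**Working it through.** **Step 1: what participation means.** Protocol 6.4.1 has transplant and device subjects "discontinued from study participation prior to the transplant operation". SAP 5.3 speaks of adverse events "that occurred between the time a subject ended the participation and subsequently returned". Protocol 5.5.1 ends participation first and places the vital-status check afterwards. In each place participation stops when the subject leaves, and vital-status follow-up comes later. On that usage SAP 4.4 excludes deaths found only by the later follow-up.

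**Step 2: inputs for size.** The documents give no death rate, exit rate or sample-size calculation, so there is no figure to reproduce. All rates here are assumptions:

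- on-study death hazard h = 0.08 or 0.12 per year;
- exit hazard d = 0.05 or 0.10 per year after month 30 (2.5 years), other than to commercial drug;
- hazard after exit = k × h.

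Time runs from parent Day 1. Month 60 of the extension is (30 + 60)/12 = 7.5 years. Parent-study exits are ignored because that study's follow-up rules are not in the documents.

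**Step 3: survival.** Censoring at exit, Kaplan-Meier tends to exp(−hT). With all deaths counted,

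S(T) = exp(−hT − d(T−2.5)) + L(T), where L(T) = ∫ from 2.5 to T of d·exp(−hu − d(u−2.5))·exp(−kh(T−u)) du.

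- Low end (h = 0.08, d = 0.05, k = 1.5, T = 5): exp(−0.40) = 0.6703, against 0.5916 + 0.0749 = 0.6664. Overstatement 0.39 points.
- High end (h = 0.12, d = 0.10, k = 4, T = 5): exp(−0.60) = 0.5488, against 0.4274 + 0.0786 = 0.5060. Overstatement 4.28 points.
- k = 1: zero at any T.

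**Step 4: share of deaths after exit.** On-study deaths by T are 1 − exp(−2.5h) + [h/(h+d)]·exp(−2.5h)·(1 − exp(−(h+d)(T−2.5))). Total deaths are 1 − S(T). At 5 years the share falling after exit is 2.4-5.0% (k = 1) to 7.0-14.9% (k = 4).

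At 7.5 years, transfer to commercial drug must be allowed for. Take an assumed transfer rate a = 0.40 per year after 2.5 years, ending observation for stayers and leavers alike. Replace d by d + a in the on-study term (both places where h + d appears). Post-exit deaths are ∫ from 2.5 to T of k·h·L(t)·exp(−a(t−2.5)) dt. The share of observed deaths is then 2.7-5.7% (k = 1) to 7.0-15.3% (k = 4), about 3-15% overall.

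**Step 5: hazard ratio.** Assume 0.084 against 0.12 per year (ratio 0.70 on study) and group sizes 2:1. The large-sample Cox estimate is the exp(b) solving ∫ [f1 − (f1+f0)·Y1·e^b/(Y1·e^b + Y0)] dt = 0. Y is the weighted fraction at risk and f the weighted death density in each group, counting all deaths.

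| Exit per year, tafamidis/tafamidis v placebo/tafamidis (same k = 2-4 in both) | 5 years, no transfer | 7.5 years, 40% a year transfer |
|---|---|---|
| 5% v 10% | 0.67-0.69 | 0.67-0.69 |
| 10% v 5% | 0.72-0.74 | 0.72-0.74 |
| 7% v 7% | 0.70 | 0.70-0.71 |

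With equal 7% exits but k differing (1.5 v 3, then 3 v 1.5), the 5-year values are 0.67 and 0.73. So the ratio moves materially if exit rates or post-exit hazards differ by group. It hardly moves if both are equal.

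**Step 6: a trap in the remedy.** Suppose stayers are censored at their own transfer date while leavers are followed to month 60. Leavers then pile up in the late risk set. At 40% a year transfer and k = 2-4, 7.5-year survival comes out 1.7-5.0 points too low. If one date caps both, the bias is zero.

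**The case against.** **SAP 4.4 may only name a data source.** It sits in a section on who is analysed, it keeps parent-study dropouts on ITT lines, and the rationale in SAP Table 1 speaks of combining data across the two studies. Protocol 9.3.1 sets no participation limit. Protocol 9 and SAP 2 both say that a major change to the primary endpoint's analysis will also appear in a protocol amendment, which favours the broader reading. This stands as a possible reading. It does not remove the point, because the SAP then contains no censoring rule at all.

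**The bias is conditional.** It is zero if leaving is unrelated to prognosis. A reader might infer that the treatment comparison is tilted towards tafamidis/tafamidis. The documents do not support that: they show no difference between groups in exits or post-exit hazard, and under the assumed imbalances the ratio can move either way.

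**The late figures are easy to overstate.** Ignoring commercial transfer, the 7.5-year share of deaths after exit would be 6-27% rather than 3-15%. Since leaving for commercial access is built into the design (Protocol 3), the larger range should not be used.

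**The follow-up is imperfect.** Outcome is to be documented where possible, and registry searches depend on local law (Protocol 6.4). Deaths may also be found more readily than survival. Both are fair, and are reasons to report completeness and keep a participation-only analysis.

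A reader might also infer that transplant and device events are lost. They are not: Protocol 9.3.1 and SAP 6.1.1 both count them as death.

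**Conclusion.** The point holds. The SAP states no censoring date for Cohort A all-cause mortality. On the usual sense of participation in these documents, deaths after early exit are left out of a tested primary endpoint, and out of cardiovascular mortality with it. The documents do not state that exclusion outright.

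The certain cost is ambiguity and, on the usual reading, lost events. Overstated survival, of about 0.4-4.3 points at 5 years, follows only if leavers have a higher hazard (1.5-4 times) at the assumed death and exit rates. A material shift in the hazard ratio needs a further difference between groups that nothing in the documents shows. The rule should be settled before the final analysis. Confidence is medium, because of the alternative reading of SAP 4.4 and because every rate is assumed.

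**What to change.** - **SAP 4.4 and 6.1.1:** state that deaths found through the protocol's vital-status follow-up count, on or off study, with censoring at the last date known alive. State how subjects who left and returned are handled.
- **Common cap:** end follow-up for everyone, early leavers included, at the earliest of 60 months, the study data cut-off, and a country-level commercial-transfer date that applies to stayers and leavers alike. Do not censor stayers at individual transfer while following leavers beyond it. Choose one anchor for the 60 months, since the protocol uses both randomization/assignment and Screening.
- **Reporting:** give vital-status completeness by treatment group, and show the participation-only analysis, censored at end of participation, as a sensitivity analysis.
- **SAP 5:** run or update the mortality analysis after the vital-status check. If the study closes early, make the check at a common cut-off date.
- **Cohort B:** state the same censoring rule. This is a clarification only, since nothing is tested there.

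Cost: SAP wording, one more programmed analysis and a completeness table. The protocol already asks for the follow-up. Downsides are a possibly later mortality table, incomplete vital status where local law limits searches, and possibly less favourable survival figures.

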# 5. GENERAL METHODOLOGY AND CONVENTIONS

The final analysis will be performed when all the subjects enrolled into the the study either discontinue (including deaths), or complete the study (60 months), or withdraws from the study due to commercial access to prescription tafamidis. Note that subjects withdrawn from the study due to commercial access to prescription tafamidis in their respective countries will be considered study completers. The study will also end before 60 months if the sponsor discontinues the study. Interim analyses may also be performed during the course of the study to allow for the reporting of data to the scientific community.

# 5.1. Hypotheses and Decision Rules

The primary objective of the study is to obtain additional, long term, safety data for tafamidis in subjects with transthyretin cardiomyopathy (ATTR-CM) and to provide investigational product, tafamidis, to ATTR-CM subjects who complete 30 months of blinded treatment on protocol B3461028 (Cohort A) and to Subjects diagnosed with ATTR-CM who have not previously participated in Study B3461028 (Cohort B). Therefore, only limited hypothesis testing ie, mortality and change from baseline in KCCQ for Cohort A subjects will be performed. All hypothesis testing will be conducted using two-sided tests with alpha = 0.05 level of significance. Since the primary objective of the study is to collect safety information, no multiplicity adjustment will be done. No hypothesis testing will be done on Cohort B subjects.

# 5.2. General Methods

For Cohort A, analyses will be performed using tafamidis/tafamidis and placebo/tafamidis treatment groups. Subjects randomized to tafamidis in parent study B3461028 and continue on tafamidis in the extension study B3461045 will be grouped as tafamidis/tafamidis. Subjects randomized to placebo in study B3461028 and randomized to tafamidis in the extension study B3461028 and randomized to tafamidis in the extension study B3461028 and randomized to tafamidis.

For Cohort B, since subjects in this Cohort will all be administered the same dose, only overall descriptive statistics will be provided.

# 5.3. Methods to Manage Missing Data

Other than standard approaches for missing dates for adverse events, no data imputation will be performed in the study. Missing data from Cohort A subjects who ended participation in B3461045 study without achieving the completion criteria of sustainable access to tafamidis by prescription, and allowed to return to the study and continue participation until they reach protocol defined study completion will not be imputed. Adverse events reported in the CRF that occurred between the time a subject ended the participation and subsequently returned will be evaluated for treatment-emergence in the same manner as adverse events that occurred during the study participation.

# 6. ANALYSES AND SUMMARIES

# 6.1. Primary Endpoint(s)

#### 6.1.1. All-cause Mortality

For Cohort A subjects, time to all-cause mortality will be calculated from Day 1 of the Study B3461028 based on the "Combined Mortality Analysis Set" as defined in Section 4.4. All-cause mortality will be analyzed using SAS Proc Lifetest; p-values will be from the log-rank test. Kaplan-Meier survival curves for each treatment group along with median survival times (if applicable) will be presented comparing tafamidis/tafamidis group with placebo/tafamidis group.

All-cause mortality will also be analyzed using Cox proportional hazards model with treatment, NYHA baseline classification, and TTR genotype (variant and wild-type) as factors. Subjects who discontinue for transplantation (ie, heart transplantation and combined heart and liver transplantation) or for implantation of a cardiac mechanical assist device, will be handled in the same manner as death. Data from subjects who drop out for a liver-only transplantation will be handled in the same manner as the data from all other censored subjects.

To examine the potential effect of including heart transplantation or cardiac mechanical assist device as "deaths" in the all-cause mortality analysis, a sensitivity analysis will be performed treating all transplantation or cardiac mechanical assist device in the same manner as any other censored observation.

For Cohort B, since subjects in this Cohort will all be administered the same dose, only overall descriptive statistics will be provided. Kaplan-Meier survival curve along with median survival time (if applicable) will be presented.

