Study B3461028 was a 30-month, Phase 3, double-blind, placebo-controlled, randomized, parallel-group trial designed to evaluate the efficacy, safety and tolerability of oral dosing of tafamidis meglumine 20 mg or 80 mg in comparison to placebo in subjects diagnosed with transthyretin cardiomyopathy and heart failure. Subject population was 441 male and female subjects aged 18 to 90 years, with ATTR-CM due to either variant, or wild type TTR. The study completed with sites in North and South America, the European Union, and Japan. The primary analysis was all-cause mortality and the frequency of cardiovascular-related hospitalizations. The primary analysis demonstrated a statistically significant reduction in the combination of all-cause mortality and frequency of cardiovascular-related hospitalizations compared to placebo. The preliminary safety data showed that tafamidis was generally well tolerated in this population and no new safety signals were identified.

The B3461045 protocol was designed as a long-term extension safety study for subjects completing 30 months of blinded treatment on Study B3461028. Given the positive results of the B3461028 study and the favorable benefit to risk profile there is a justification to provide patients with an option for early access to tafamidis. Consequently, the B3461045 study protocol will be amended herein to include an additional cohort of patients with ATTR-CM who have not previously participated in the B3461028 parent study. The purpose of the additional cohort is to provide these patients early access to tafamidis, until local availability by prescription for the ATTR-CM indication.

Additionally, a new formulation which is bioequivalent to tafamidis meglumine 80 mg has been developed and is presented as tafamidis 61 mg (as the free acid). This formulation, where available, will replace the tafamidis meglumine 80 mg dose after protocol amendment 3.

Objectives and Endpoints:

Primary Objectives:

- To obtain additional, long-term, safety data for tafamidis in subjects with transthyretin amyloid cardiomyopathy (ATTR-CM).
- To provide investigational product, tafamidis, to enrolled subjects until local availability by prescription for the ATTR-CM indication.

Primary Endpoints:

Safety as measured by:

- All-cause mortality.
- Incidence of treatment-emergent adverse events.

Other Endpoints:

- Cardiovascular-related mortality.
- Frequency of all-cause hospitalization.

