9.1. Sample Size Determination

There is no formal sample size calculation for this protocol. Subjects who meet enrollment criteria are eligible; up to 2000 subjects are expected to enroll in Protocol B3461045.

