# **1. VERSION HISTORY**

This Statistical Analysis Plan (SAP) for Study B3461045 is based on the protocol global amendment 4 dated 09 August 2019 and United States specific PACL dated November 26, 2019.

SAP Version	Change	Rationale
1	Not Applicable	Not Applicable
2	Changes are captured in the summary of changes table (Table 1)	Amendment to make minor corrections to the SAP
3	Amended to reflect the protocol amendment 3. Changes are captured in summary of major changes table (Table 1)	Amended to reflect the protocol amendment 3
4	Amended to reflect the protocol amendment 4. Changes are captured in summary of major changes table (Table 1)	Amended to reflect the protocol amendment 4
5	Added analyses of select endpoints excluding data from site 1121 (all subjects) to address a potential quality event identified at the site.	Amended to add analyses to address a potential quality event identified at site 1121

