#### **Appendix 2. STATISTICAL METHODOLOGY DETAILS**

Sample SAS code for time to event analysis is given below.

PROC LIFETEST DATA=xxx PLOTS=(s) graphics; TIME dur \*status(0); STRATA trt; RUN;

PROC PHREG DATA=xxx; MODEL dur\*status(0)=trt genotype NYHAbase/ ties=EXACT; RUN;

Sample SAS code to fit the mixed model repeated measures is given below. The response variable Y is the change from baseline at the study visits.

PROC MIXED DATA=xxx METHOD=REML EMPIRICAL; CLASS pid center trt visit genotype; MODEL y= ybase trt visit genotype trt \*visit; RANDOM int/SUBJECT=center; REPEATED visit /SUBJECT= pid (center) r type=UN; RUN;

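### The main mortality p-value ignores genotype and NYHA class although the SAP's own Cox model adjusts for both: a cheap improvement to a valid test, not an error

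*SAP*

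**What the plan says.** SAP 6.1.1 takes the Cohort A all-cause mortality p-value from a log-rank test: "All-cause mortality will be analyzed using SAS Proc Lifetest; p-values will be from the log-rank test". The sample code in SAP Appendix 2 has "STRATA trt; RUN" in PROC LIFETEST. Without a `GROUP=` option, that statement only defines the arms being compared, so the test is unstratified. Protocol 9.3.1 prescribes the same test.

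The next paragraph of SAP 6.1.1 adds covariates: "All-cause mortality will also be analyzed using Cox proportional hazards model with treatment, NYHA baseline classification, and TTR genotype (variant and wild-type) as factors". Protocol 9.3.1 has genotype but not NYHA in its Cox model. SAP 6.2.1 carries the approach over: "cardiovascular-related mortality will be analyzed separately similar to all-cause mortality detailed in Section 6.1.1".

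SAP 5.1 confines testing to Cohort A mortality and KCCQ: "All hypothesis testing will be conducted using two-sided tests with alpha = 0.05 level of significance". It makes no multiplicity adjustment. Protocol 9.1 gives no power: "There is no formal sample size calculation for this protocol".

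The parent result is already reported in the Protocol Summary (Background and Rationale): "The primary analysis demonstrated a statistically significant reduction in the combination of all-cause mortality and frequency of cardiovascular-related hospitalizations compared to placebo". The current SAP "is based on the protocol global amendment 4 dated 09 August 2019", so it was written with that result known.

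**The concern.** The sponsor judged genotype and NYHA class worth adjusting for when estimating the mortality HR, yet the p-value beside that HR ignores both. The KCCQ model also adjusts, for genotype and baseline score. The mortality log-rank test is therefore the one planned test without covariates, and it serves a primary endpoint.

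Two things are at stake. First, when a strong prognostic factor is left out of a survival comparison, the marginal treatment effect is pulled toward no difference and the test becomes less sensitive. Second, the report may show an adjusted HR whose interval excludes 1 next to a non-significant p-value, or the reverse. SAP 6.1.1 makes the log-rank test the source of p-values but does not say how to read such a conflict.

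**Working it through.** **No plan figure to reproduce.** The documents state no event count, power or covariate effect for mortality. The check is a comparison of the texts, plus simulation for scale.

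**The tests.** With observed minus expected deaths U and variance V:
- planned: Z = U / √V, computed over all subjects together;
- stratified: Z = Σ U_s / √(Σ V_s), summed over genotype × NYHA strata s;
- Cox: Wald test for treatment, with genotype and NYHA as factors.

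**Inputs.** From the documents: 441 parent-study subjects (Protocol 1.2) and two-sided alpha 0.05 (SAP 5.1). Assumed:
- 265 tafamidis and 176 placebo subjects, with a mean placebo hazard of 0.18 per year;
- a constant HR of 0.70;
- 25% variant genotype and 33% in the higher NYHA class;
- 80% followed to Month 60, and the rest censored at Month 30.

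**Hand check with no covariate effects.**
- Placebo: 0.8(1 − e^−0.90) + 0.2(1 − e^−0.45) = 0.547; × 176 = 96.3 deaths.
- Tafamidis, hazard 0.126: 0.8(1 − e^−0.63) + 0.2(1 − e^−0.315) = 0.428; × 265 = 113.4 deaths.
- Total: 209.7 deaths.
- Schoenfeld: √(209.7 × 0.601 × 0.399) × |ln 0.70| − 1.96 = 7.09 × 0.357 − 1.96 = 0.57, which is power of about 72%. The simulation gives 72.9%.

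**Simulated power (%), 20,000 trials per row, Monte Carlo SE about 0.3 points.**

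| Assumed HR, genotype / NYHA | Unstratified | Stratified | Adjusted Cox | Stratified minus unstratified | Cox minus unstratified |
|---|---|---|---|---|---|
| 1 / 1 | 72.9 | 72.5 | 72.7 | −0.4 | −0.2 |
| 1.25 / 1.5 | 71.3 | 72.4 | 72.5 | 1.1 | 1.2 |
| 1.5 / 2.0 | 67.9 | 70.9 | 71.2 | 3.0 | 3.3 |
| 2.0 / 2.5 | 61.9 | 68.7 | 69.3 | 6.8 | 7.4 |
| 2.0 / 3.5 | 56.4 | 67.1 | 67.7 | 10.7 | 11.3 |

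**Sensitivity.**
- With follow-up to 90 months, or an HR of 0.70 that becomes 0.85 after Month 30, the last three rows show losses of about 4, 8 and 11 to 14 points.
- With three NYHA classes (six strata), stratifying costs 0.7 points if neither factor matters. It gains 2.6 and 6.0 points in the two prognostic cases tried.
- A separate simulation used about 240 to 277 deaths and a tafamidis share of 0.50 to 0.667. Stratifying gained about 0 points (1/1), 0.2 to 1.6 (1.5/1.5), 1.7 to 3.7 (1.5/2), 4.4 to 5.6 (2/2) and 9.2 to 11.8 (2/3).

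**Disagreement.** The share of trials in which the log-rank p-value and the adjusted Cox result fall on opposite sides of 0.05 is 1.8% (1/1), 9.0% (1.5/2.0) and 18.1% (2.0/3.5) for the unstratified test. For the stratified test it is 1.7 to 3.0%.

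**Type I error, test fixed in advance.** It is 4.9 to 5.2% unstratified, 5.1 to 5.2% stratified and 5.0 to 5.1% Cox. If the parent randomization was itself stratified on both factors, which the documents do not say, the unstratified test is conservative: 4.3% (1.5/2.0) to 3.0% (2.0/3.5). Picking the smaller of the two log-rank p-values after seeing both would give 5.6 to 7.5%.

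**Code.** The PHREG sample has no `CLASS` statement, although 6.1.1 calls the covariates factors; the MIXED sample in the same appendix has one. A numeric two-level variable fits the same either way. A numeric NYHA variable with more than two levels would be fitted as a linear trend.

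**The case against.** The case for leaving the test alone is substantial. The test is valid, and protocol and SAP agree on it. The more sensitive analysis is already planned one paragraph later and will be reported. The study is mainly descriptive, no success criterion hangs on p < 0.05, and an unadjusted test beside an adjusted estimate is ordinary reporting. Every input to the power figures except 441 is assumed. A late change also carries risk: under the assumed hazards, roughly 52 to 67% of deaths fall in the parent period, which has already been read out. SAP 5 and 7 further allow interim analyses of extension data.

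All of this stands, and it limits the point to an improvement. It does not remove the inconsistency between p-value and HR, which costs little to resolve.

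A reader might also infer more than the documents support:
- **That the test is wrong or inflates type I error.** It does not; at worst it is conservative.
- **That the analysis fails to match the randomization strata.** The genotype stratification in Protocol 5.1.1 concerns treatment assignment in the extension. The mortality contrast comes from the parent randomization, whose factors are not given.
- **That baseline NYHA is undefined.** SAP 6.1.1 does not name the study, but Table 2 in SAP 3.4 ties mortality analyses to the B3461028 baseline. The analysis set also includes subjects who never entered the extension, so only the parent value works.
- **That the absence of NYHA from Protocol 9.3.1 is a contradiction.** Both documents allow the SAP to modify the protocol's plans. Aligning the two is tidying.

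**Conclusion.** The point holds as a cheap improvement. The planned log-rank test is sound, but it sets aside two covariates that the same section already uses. Under the assumed inputs, the cost to the main mortality p-value is about 0 points of power if genotype and NYHA are not prognostic, 1 to 4 if modestly so, and about 7 to 11 if strongly so. Some long-follow-up or waning-effect scenarios reach 14. The documents cannot place the trial within that range, so no single figure should be quoted as its loss. Possible disagreement between the p-value and the adjusted HR is the more practical reason to act. The same reasoning applies to cardiovascular mortality.

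**What to change.** Before the final analysis, in a dated SAP amendment:

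1. Name one main p-value for all-cause mortality, and likewise for cardiovascular mortality. The simplest choice is the treatment test from the existing Cox model with genotype and B3461028-baseline NYHA, because it adds no new model. The log-rank test stratified by the same factors (`STRATA genotype NYHAbase / GROUP=trt`) is within 1 point of power and would also serve. Only one should be named. In the by-genotype repeats (SAP 6.3), NYHA alone remains as covariate or stratum.
2. Keep the unstratified log-rank p-value in the report, beside the Kaplan-Meier curves and labelled supportive.
3. State that parent results, and any interim extension results, were known when the change was made.
4. Amend Protocol 9.3.1 to match. Protocol 9 and SAP 2 both call for a protocol amendment when the analysis of a primary endpoint is materially changed.
5. State in 6.1.1 that NYHAbase is the parent-study baseline class, and add `CLASS trt genotype NYHAbase` to the PHREG code.

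The cost is wording, a protocol amendment and a few lines of code; no new data are needed. There are three downsides. Under 1 point of power is lost if neither factor is prognostic. The main p-value no longer corresponds to the unstratified curves. The change comes after parent data were seen, which is why it must be dated and disclosed and must name a single test in advance.
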